Protocol

Study Title

Feasibility Trial of the TELL Tool Intervention

NCT number:

NCT04841967

Document Date: Updated 04-06-2023

Human Subject Protections/Institutional Review Board Approval:

University of Illinois Chicago IRB Protocol # 2020-1086
University of Michigan Protocol # HUM00230985

STUDY DESIGN

Narrative Study Description

The proposed research is clinically relevant as a paradigm shift is underway in medical reproduction. The secrecy that has historically shrouded the practice of gamete donation is lifting. Technology, especially in the form of direct-to-consumer genetic testing (e.g., Ancestry.com, 23andMe), is rapidly removing any illusion of secrecy and anonymity in gamete and embryo donation families. To preempt trauma to modern families due to DR parents' non-disclosure of their children's donor origins and promote shared knowledge of actual genetic heritage our study will provide an accessible and self-administered decision support tool (TELL Tool) to assist DR parent's disclosure to their child(ren). This project aims to examine the feasibility, acceptability, and preliminary effects of the TELL Tool intervention in a pilot randomized-controlled feasibility trial. The objective and aims are consistent with the goals of the NIH R34 program and the TELL Tool will be the first in the U.S. to address health promotion for DR parents and their donor-conceived children, a scientific priority of NINR.

Assignment of Participants

Our recruitment pool will consist of a convenience sample of DR parents and clinicians actively recruited through a broad-based, multifaceted plan. Interested DR participants will be asked to contact the Principal Investigator (PI) to schedule a phone interview for targeted recruitment screening. During the initial phone interview all potential DR parents will have the study fully explained and permission will be sought to screen for eligibility. Interested participants will be screened for eligibility by determining whether they are DR parents who used donated eggs, sperm, or embryos to have child(ren) and have not told their donor-conceived child(ren) about their donor origins. If the potential participant meets all eligibility requirements and expresses interest in the study, they will be directed to the study website and provided with a unique code that will allow them access to complete the online Informed Consent. Both the DR parents and practicing clinicians will complete an online Demographic Form immediately after providing Informed Consent. The form asks questions about personal characteristics such as age, race/ethnicity, and education. There are several questions that are specific to DR parents such as questions about the type of donation they used (e.g., donated egg or donated sperm) and questions specific to practicing clinicians such as what is their current professional role (e.g., nurse, physician). These questions are in accordance with our plans to establish a wide range of both DR parent and practicing clinician participants as well as enhancing our understanding of our sample of participants.

Group Randomized Trial

The study is a pilot randomized-controlled trial in which the units of assignment are DR parent groups and the units of observation are members of two groups (DR **intervention** parents and **attention-control** parent groups). Eligible DR parents who have consented and completed the Demographic Form, will be randomized into two groups (either the TELL Tool **intervention** group or the **attention-control** eBook group) using a permuted block approach that is stratified by the age categories of the DR parent's children and using an online (REDCap) randomization module.

Delivery of Interventions

During the initial phone recruitment interview, the PI will explain the nature of the study, risks, benefits, length, voluntary nature of participation, and the right to discontinue participation at any time without consequences and will screen potential participants for eligibility according to the inclusion and exclusion criteria. DR parents that are screened and meet eligibility requirements will be informed of the study website and provided the URL and a unique study code, which will serve as a portal for enrolling and providing demographic information and obtaining Informed Consent, completing the online Surveys and administering the TELL Tool or eBook interventions.

DR parents that are randomized to the TELL Tool **intervention group** will complete four online modules that are based on our prior research with DR parents. These four modules center on DR parents' cognitive, emotional, moral and relationship concerns that arise when DR parents consider whether to tell or not to tell their child(ren) about their donor-conception origins. The TELL Tool is designed using several strategies that enable DR parents to engage with the online materials. In addition, the TELL Tool is custom-tailored for DR parents by the type of family (for example a single-parent family versus a two-parent family), the type of donation (egg, sperm, or embryo) the DR parents used, and the age(s) of the DR parent's child or children. It will take DR parents about 60 minutes to complete the TELL Tool online modules. Immediate post-intervention DR parents will be directed to the post-test web page to complete (1) the *Outcomes Survey** measuring our (preliminary) outcomes for intention, competence, and anxiety about disclosing the donor conception to their children, and (2) the *Acceptability of the TELL Tool or eBook Survey.*** Then, at 4-weeks and 12-weeks post-intervention, DR parents will complete the *Survey on Actual Parental Disclosure.*

The DR parents that are randomized to the **attention-control eBook group** will complete a 60-minute online program that has up-to-date information about strategies that promote good parenting skills. The eBook has graphics and photographs that make it visually engaging for DR parents and easy to use. Immediate post-attention control, DR parents will be directed to the post-test web page to complete the (1) *Outcomes Survey** measuring our (preliminary) outcomes for intention, competence, and anxiety about disclosing the donor conception to their children, and (2) the *Acceptability of the TELL Tool or eBook Survey.*** Then, at 4-weeks and 12-weeks post-attention control, DR parents will complete the *Survey on Actual Parental Disclosure.**** After all data are obtained, we will complete Year 1 analyses and make modifications to the TELL Tool, eBook, and protocols, as needed.

In Year 2 of the study, Cognitive Interviews will be conducted on a selected sub-sample of 10 DR parents and 10 practicing clinicians. Participants will be asked to complete individual interviews where they will be asked specific questions about how the TELL Tool and eBook and its design and administration can be improved further. We will use an Interview Guide, developed for the study that builds on our prior research and also uses guidelines and standards for developing decision aids to elicit information from DR parents and clinicians. In keeping with good scientific practice, the PI will use an Interviewer Summary Form to make field notes about observations when DR parents and clinicians are completing the cognitive interviews and interacting with the TELL Tool and/or eBook. The information we obtain from the Cognitive Interviews and from the Interviewer Summary Form will allow us to make final revisions and improvements to the TELL Tool, eBook, and/or the study protocol in Year 2.

Measures

Primary Outcome

*****Survey on Actual Parental Disclosure.** This 6-item survey is an accepted method for obtaining meaningful information about actual DR parent's disclosure about the donor-conception origins to their child(ren). Within this survey, we will use the question "*Have you told your child or one or more of your children about their donor conception?*" [Response options: Yes or No] to establish whether DR parents have/have not disclosed to their child(ren).

Sample Size

We anticipate recruiting 75 DR parents in order to retain 60 DR parents through follow-up, conservatively assuming 80% retention given the 86% retention rate in our 12-year pilot study. The planned recruitment of 75 DR parent participants will allow point estimates and confidence intervals of our feasibility metrics (e.g., recruitment and retention) and means and standard deviations by treatment arm in outcome measures.

For the cognitive interview sample of 20 participants, we will include a sub-sample of 10 DR parents from our larger sample of DR parents, based on their 1) responses to the *Acceptability of the TELL Tool or eBook Survey* (e.g., participants who give detailed responses) and 2) in consideration of the maximum variation sampling plan (e.g., DR parent's gamete donation type, parent type, age category of the children to be told, and the 10% minority DR parent composition requirement). Maximum variation sampling will also be used to obtain the sample of 10 practicing clinicians for the cognitive interviews to allow for representation of nurses, physicians, psychologists, and social workers. The sample size for the 20 cognitive interviews (10 DR parents/10 clinicians) is consistent with International expert recommendations for decision aid development; other investigators that have developed decision aids; the needs of the study, and the acceptability evaluation and cognitive interviews used successfully in the development of the CHOICES intervention, a similar reproductive intervention.

Statistical Analysis Plan

We will emphasize descriptive statistics such as means, standard deviations, effect sizes, medians, interquartile ranges, frequencies, and percentages to demonstrate the feasibility of recruitment, adherence, retention, acceptability, and treatment effects of change in outcomes between the TELL Tool and the attention control eBook groups. Confidence intervals will be used to estimate a plausible range of values for these estimates.

Because our data analysis plan includes looking ahead to a full efficacy trial where we will use a mixed-effect model for repeated measures (MMRM), which is recommended for primary analysis of clinical trials with continuous endpoints using an intent-to-treat approach. We have considered the data analysis needed for our future efficacy trial in this proposed study. Noteworthy, the MMRM model can accommodate correlations due to dyad respondents and repeated measurements and handles missing outcomes with a maximum likelihood method appropriate when data are assumed to be missing at random. We will examine the planned model using our pilot data to assess if the statistical plan will need modification.

We will examine the extent of missing data and determine correlates of missingness through associations with our other measures and through our qualitative interviews. Including predictors of missing data will support the missing at random assumption in our future efficacy trial. Other goals of quantitative analyses will be to examine measurement scale psychometric properties, including adequate variability and ability to detect change. We will examine the pattern of outcomes over time to identify the optimal endpoint for outcome assessment. Purported mediators will be examined for change over time and change scores of mediators and outcomes will be correlated. In addition, we will explore our pilot results for trends to identify potential moderators such as age group of the child. These analyses will further inform future improvement of the TELL Tool.

Primary Purpose

The primary purpose of this pilot trial is feasibility because our objective is to examine the feasibility, acceptability, and preliminary effects of the TELL Tool intervention in a pilot randomized-controlled feasibility trial.

STATISTICAL DESIGN AND POWER

In this mixed-method study, we will use a 1:1 parallel groups randomized-controlled trial with targeted recruitment of 60 DR parents. A parent dyad will count as 1 DR parent as does a single parent or a family with multiple donor-conceived children. In view of our prior research with DR parents, we expect about 90% of the 60 DR parent participants ($n = 54$) will be dyadic DR parents (108 individuals) and 6 individuals will comprise 6 “single” DR parents in the sample for a total of 114 DR parent participants. Because this is a pilot randomized-controlled feasibility trial, the focus of the analyses will be on the feasibility of study procedures, however, our planned enrollment of 75 DR parent participants will allow point estimates and confidence intervals of our feasibility metrics (e.g., recruitment and retention) and means and standard deviations by the intervention (TELL Tool) and attention control (eBook) groups in our primary outcome measure.

04-06-2023 Update

A reliance agreement was obtained between the IRBs from the University of Illinois Chicago and the University of Michigan as [name] is now [name] at the University of Illinois Chicago and also a Professor at the University of Michigan.

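### Allocation is stratified by child age category, but no between-arm estimate is said to account for that stratum; if it is ignored, the confidence intervals can be wider than they need to be

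*Combined protocol and SAP*

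**What the plan says.** Under Group Randomized Trial, families are randomized through REDCap using a "permuted block approach that is stratified by the age categories of the DR parent's children". Under STATISTICAL DESIGN AND POWER, the allocation ratio is 1:1 and the family is the counting unit: "A parent dyad will count as 1 DR parent as does a single parent or a family with multiple donor-conceived children".

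The Statistical Analysis Plan is mainly descriptive. It includes effect sizes for "treatment effects of change in outcomes between the TELL Tool and the attention control eBook groups", and adds that "Confidence intervals will be used to estimate a plausible range of values for these estimates". No stratum or covariate is named for these contrasts, and the confidence level and method are not given.

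The same section describes an MMRM meant for the later efficacy trial and to be tried on the pilot data. It is introduced as "recommended for primary analysis of clinical trials with continuous endpoints using an intent-to-treat approach". The text covers dyad and repeated-measure correlation and missing data, but lists no stratum term. Child age appears in the analysis once: "we will explore our pilot results for trends to identify potential moderators such as age group of the child".

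The primary outcome, under Measures, is a Yes/No disclosure item.

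**The concern.** Stratified blocks make the arms alike on child age, so age contributes less to the chance difference between arms. A two-sample standard error does not know this and still counts the between-stratum variation as noise. The difference is estimated without bias, but the reported interval covers more than its nominal level and is wider than the design warrants.

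Nothing else in the plan fills the gap. A moderator search asks whether the effect varies with age; it does not adjust the main contrast. The MMRM has no stated covariates and is described for continuous endpoints, so it would not supply the interval for a Yes/No outcome. The plan is silent here and does not rule the stratum out.

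The plan gives reason to think age may matter: besides stratifying on it and naming it as a moderator, it tailors the TELL Tool to "the age(s) of the DR parent's child or children". At stake is how informative the preliminary-effect intervals are with about 60 retained families.

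**Working it through.** **Inputs from the documents.** 75 recruited, 60 retained, 80% retention (Sample Size); 1:1 allocation (STATISTICAL DESIGN AND POWER); permuted blocks stratified by child age (Group Randomized Trial). The plan's figure reproduces: 60 / 0.80 = 75. It is not in dispute.

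**Assumed, because the documents do not give them.** Three strata, blocks of 4, 95% intervals, one record per family, random loss to follow-up, the disclosure rates, and the share of variance R² that age stratum explains.

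**Closed form, perfect balance, 30 per arm.** For a risk difference with equal strata, unadjusted SE = √[p̄(1−p̄)·2/30]. Adjusted SE replaces p̄(1−p̄) with the mean of p(1−p) over strata. At rates 5/25/55%:

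- p̄ = 0.2833 and p̄(1−p̄) = 0.2031
- mean within-stratum variance = (0.0475 + 0.1875 + 0.2475)/3 = 0.1608
- R² = 1 − 0.1608/0.2031 = 0.208
- SE = 0.1163 unadjusted and 0.1035 adjusted, ratio 1.124

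**Simulation with 20% loss.** 20,000 runs per scenario, no treatment effect, linear risk difference with a t interval, without and with stratum indicators. Strata are equal unless noted.

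| Stratum rates | Width, unadjusted | Width, adjusted | Unadjusted wider by |
|---|---|---|---|
| 5/25/55% | 0.466 | 0.416 | 12% |
| 5/25/55%, strata 50/30/20% | 0.421 | 0.370 | 14% |
| 10/30/50% | 0.474 | 0.445 | 7% |
| 10/20/30% | 0.412 | 0.405 | 2% |
| 20/25/30% | 0.448 | 0.448 | 0% |
| 25/25/25% | 0.447 | 0.449 | −0.5% |

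In the first row, coverage is 96.8% unadjusted and 95.1% adjusted. The true spread of the two estimators is close (SD 0.1070 and 0.1045), while the reported SEs are 0.1165 and 0.1038. The unadjusted SE thus overstates its own SD by a factor of 1.089, somewhat less than the perfect-balance ratio because dropout disturbs the balance. Most of the excess width is overstated uncertainty, not a poorer point estimate.

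Repeating the exercise with a true difference of 0.20 (8,000 runs) gave the same pattern. Width ratios were 1.06 for control rates of 10/30/50% and 1.13 for 5/25/60%; bias in the risk difference was at most 0.004.

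**Continuous scales, 30 per arm, half-width in SD units.** Unadjusted: t(58)·√(2/30) = 0.517. Adjusted: t(56)·√[(2/30)(1−R²)].

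| R² | Adjusted half-width | Unadjusted wider by |
|---|---|---|
| 0 | 0.517 | 0% |
| 0.10 | 0.491 | 5% |
| 0.20 | 0.463 | 12% |
| 0.30 | 0.433 | 19% |

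Simulated unadjusted coverage rose from 95.2% at R² = 0 to 97.6% at R² = 0.30. Adjusted coverage stayed between 94.4% and 95.3%.

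**The case against.** The strongest reply is that nothing turns on this. The trial is a feasibility pilot with no hypothesis test, power figure or effect-based progression rule. An interval 0.47 wide and one 0.42 wide are both imprecise, and the error is on the safe side. That stands as a limit on importance.

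The size is also open to challenge. The 12–14% figures need a steep age gradient. Every enrolled parent is a non-discloser at entry and follow-up ends at 12 weeks, so uniformly low rates are plausible. At 2/8/15% the widths are 0.282 and 0.278, and at 5/10/20% they are 0.328 and 0.323, a loss of about 1.4%. This is fair: the gain may be close to nil.

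For the scales, the plan speaks of effects on change. Change scores remove stable age differences, so the relevant R² is that of age on change, which may be below 10–30%. That also stands.

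Finally, the conservative direction assumes one record per family. STATISTICAL DESIGN AND POWER also counts 114 individuals. Analysing partners as independent would push the interval the other way and could outweigh the stratum effect. This is a condition on the result.

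These points bear on how much is lost. They do not supply an adjusted contrast, and neither the moderator search nor trying out the MMRM does so.

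**Conclusion.** The concern holds. Allocation uses child age category and no planned between-arm estimate is said to use it. If the stratum is left out, mean and risk differences remain unbiased and their intervals are conservative. In the settings examined, the excess width runs from none to about 14% for disclosure and up to 19% for a continuous scale with R² of 0.30. It depends on how strongly child age predicts outcome, which the documents do not say, and on one record per family and random dropout.

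The consequence is limited to precision in a descriptive pilot. The point is still worth acting on because the stratum must already exist for randomization and using it costs almost nothing. The result does not carry over to odds ratios, where adjustment changes the quantity estimated and need not narrow the interval.

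**What to change.** State in the Statistical Analysis Plan that between-arm estimates account for the randomization stratum as recorded in REDCap.

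- **Disclosure:** report a stratum-adjusted risk difference from a linear model with stratum indicators, or by Mantel-Haenszel. Mantel-Haenszel with the Sato variance covered 94.1–94.3% in four equal-strata scenarios, so the regression form is slightly better calibrated at this size.
- **Intention, competence and anxiety:** include stratum as a covariate, also in the MMRM tried on the pilot data.
- **Sparse strata:** merge by a rule stated in advance.

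As a secondary clarification, write down the age categories and whatever rule places a family with children in more than one category, and use the same value in the analysis. No particular rule is needed, and this gap does not itself affect interval validity.

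The cost is one or two sentences and one model term. With three strata, 2 degrees of freedom are lost, widening the disclosure interval by about 0.5% if age has no effect; with five strata the figure is about 1%.

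### The primary disclosure item has no reference date and the only non-disclosure check described is the pre-consent phone screen, so telling before randomization is counted as an outcome

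*Combined protocol and SAP*

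**What the plan says.** All references are to the combined protocol and SAP.

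- **Outcome item (Measures, Primary Outcome).** Of the disclosure survey's six items, one Yes/No question classifies the parent as having disclosed or not: "Have you told your child or one or more of your children about their donor conception". No start date is attached to it. The other five items are not described.
- **Eligibility (Assignment of Participants).** Parents qualify if they "have not told their donor-conceived child(ren) about their donor origins". This is determined by phone: "During the initial phone interview all potential DR parents will have the study fully explained and permission will be sought to screen for eligibility". Delivery of Interventions likewise places screening in that call.
- **From screen to randomization (Assignment of Participants; Group Randomized Trial).** An eligible parent receives a website code, consents online and fills in the Demographic Form. Then "Eligible DR parents who have consented and completed the Demographic Form, will be randomized into two groups". The form directly follows consent, but no limit is given for the time from call to consent or from form to randomization. Its content is described by example: "The form asks questions about personal characteristics such as age, race/ethnicity, and education", plus items such as donation type. Disclosure status is not among the examples.
- **Timing of the disclosure survey (Delivery of Interventions).** "Then, at 4-weeks and 12-weeks post-intervention, DR parents will complete the" disclosure survey. The eBook arm has the same schedule. No baseline administration is described.

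**The concern.** A Yes at week 4 or 12 should mean that the parent moved from not having told to having told during the trial. That needs either a confirmed No at randomization or a question that asks only about the period since then. The plan as written has neither.

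The phone call explains a study about disclosure in full, and it could itself prompt some parents to tell. If a parent does so before being randomized, the undated item records Yes at both follow-ups, and nothing described in the plan separates that answer from a new disclosure.

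A smaller ambiguity sits beside this. The outcome is Yes once any one child has been told, whereas the eligibility wording does not expressly say how a family is handled when one of several children already knows. Statistical Design and Power anticipates families with more than one donor-conceived child.

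At stake is how cleanly the two disclosure rates, and the contrast between them, can be read. The Statistical Analysis Plan section does intend to report effect sizes and treatment effects, even though the trial is primarily about feasibility.

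**Working it through.** **The plan's own figure.** Sample Size recruits 75 to retain 60 at 80% retention: 60 / 0.80 = 75. This reproduces and does not depend on the present point. The plan states no disclosure rates, effect size or power, so there is no further figure to reproduce.

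**Sequence as described.** Phone screen (status must be No) → website, consent and Demographic Form → randomization → program → survey at 4 and 12 weeks. Disclosure status is described as established at the first step and next at the last. Telling between the first step and randomization is pre-randomization telling that the primary item scores as Yes.

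**Illustration.** Inputs, all assumed:

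- p₁ = 0.30 (TELL Tool) and p₀ = 0.10 (eBook): true 12-week disclosure among families still at No when randomized.
- f: the share already at Yes when randomized, the same in both arms in expectation; f = 0, 0.05, 0.10, 0.20.

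Formulas:

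- Observed rate in an arm = f + (1 − f)p.
- Observed risk difference = (1 − f)(p₁ − p₀), because f cancels.
- Odds ratio = [a/(1 − a)] / [b/(1 − b)], with a and b the observed TELL Tool and eBook rates.

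For f = 0.10: TELL Tool 0.10 + 0.90 × 0.30 = 0.37; eBook 0.10 + 0.90 × 0.10 = 0.19; difference 0.90 × 0.20 = 0.18; odds ratio (0.37/0.63) / (0.19/0.81) = 2.50.

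| f | TELL Tool | eBook | Risk difference | Odds ratio |
|---|---|---|---|---|
| 0 | 30% | 10% | 0.20 | 3.86 |
| 5% | 33.5% | 14.5% | 0.19 | 2.97 |
| 10% | 37% | 19% | 0.18 | 2.50 |
| 20% | 44% | 28% | 0.16 | 2.02 |

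Both rates rise, the eBook rate by more (9 points against 7 at f = 10%), which is why the difference shrinks.

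**Set against the pilot's precision.** With 60 retained and 1:1 allocation there are 30 per arm. At 30% vs 10% the 95% confidence half-width for the difference is 1.96 × √(0.30 × 0.70/30 + 0.10 × 0.90/30) = 1.96 × 0.10 = 0.196. A shift of 0.01 to 0.04 is small beside that.

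**The case against.** The case on the other side is substantial, and most of it limits the point rather than removing it.

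- **The window may be short and f small.** Only the intervals from call to consent and from form to randomization are open. The illustrated fractions equal half, all or twice the assumed 12-week eBook rate of 10%, and the documents support none of them. This stands: the size is unknown. The odds ratio also makes the dilution look larger than the risk difference does.
- **Partly told families.** A reader might infer that a parent who has told one child but not another will be admitted and score Yes from the start. The documents do not support that. The ordinary reading of the eligibility wording, which covers one child or several, is that none has been told. What remains is that the case is not expressly excluded.
- **Telling after randomization but before the program.** A reader might count this as contamination too. It is not an error: it follows allocation and belongs in the intention-to-treat comparison.
- **Bias towards one arm.** A reader might infer that the result is tilted. Pre-randomization telling cannot depend on allocation, so it is balanced in expectation.
- **Planning of the efficacy trial.** A reader might infer that the pilot exists to supply disclosure rates for the later trial. No section says so. Primary Purpose names feasibility, and the Statistical Analysis Plan section looks ahead to a mixed model for continuous endpoints.
- **Undescribed content.** The Demographic Form is described only by example and five survey items are not shown, so baseline status or a date of telling might be captured there. That is possible, but the plan does not say so, and the outcome rests on the single item.

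The core is untouched: the item is undated, no repeat check is described, and no rule sets aside earlier telling.

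**Conclusion.** The point holds as a cheap improvement of low severity. Followed as written, the plan counts any telling between the phone screen and randomization as a trial outcome in either arm. The expected effect is higher rates in both arms and a modestly diluted contrast. Under assumed true rates of 30% vs 10%, the risk difference falls from 0.20 to 0.16 even if one family in five was already at Yes, and only to 0.19 if one in twenty was. These figures rest on assumed rates, an assumed f, and equal f in the two arms. The documents cannot show which value of f, if any, is realistic. The validity of the randomized comparison is not in question.

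**What to change.** 1. Add the same Yes/No question, worded to cover all of the family's donor-conceived children, as the last item on the online form before randomization. Let the REDCap module randomize only families answering No. This also settles how partly told families are handled.
2. At weeks 4 and 12, date the item from randomization: *Since [randomization date], have you told …*. This continues to count telling after randomization but before the program, as an intention-to-treat comparison should.
3. Report how many families are turned away at step 1. That count is a direct estimate of f.

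The cost is one question on an existing form, one gate in the randomization module and a wording change. A few phone-eligible families would not be randomized, so the reported screen-to-enrolment rate may be slightly lower. The target of 75 recruited and 60 retained does not change. If data have already been collected, the sponsor should state whether baseline status or the date of telling was recorded and, if so, report pre-randomization telling separately.

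### Arm effects on intention, competence and anxiety are framed as change; adjusting the post-program score for the pre-program score would generally give narrower intervals, and when that pre-program score is taken is not stated

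*Combined protocol and SAP*

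**What the plan says.** The only wording on how the arms will be compared on outcomes is in the Statistical Analysis Plan section, which lists "treatment effects of change in outcomes between the TELL Tool and the attention control eBook groups" among the things that descriptive statistics, including effect sizes, will show. It adds: "Confidence intervals will be used to estimate a plausible range of values for these estimates". Later in the same section: "Purported mediators will be examined for change over time and change scores of mediators and outcomes will be correlated". No baseline covariate and no adjusted difference is named anywhere.

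The scale outcomes are in the Outcomes Survey, which measures "outcomes for intention, competence, and anxiety about disclosing the donor conception to their children". Delivery of Interventions places it after the program: "Immediate post-intervention DR parents will be directed to the post-test web page to complete", with parallel wording for the eBook arm. Before allocation, the Group Randomized Trial section mentions only consent and the Demographic Form: "Eligible DR parents who have consented and completed the Demographic Form, will be randomized into two groups". Assignment of Participants describes that form: "The form asks questions about personal characteristics such as age, race/ethnicity, and education". No administration of the three scales before the program is described. The 4-week and 12-week contacts use only the disclosure survey.

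A mixed model for repeated measures (MMRM) is intended for the later efficacy trial and will be tried on the pilot data. How a baseline score would enter it is not stated.

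**The concern.** Read naturally, the plan will report between-arm differences in change with confidence intervals. A change score subtracts the whole pre-program score, even where that score predicts the post-program score only weakly. In a randomized comparison the same two scores can instead be used by regressing the post-program score on arm and pre-program score. Both estimates are unbiased, and the second is generally the more precise.

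Preliminary effects are a stated objective of the pilot, and the plan sets no power target. Interval width is therefore the main measure of what the pilot shows about effects on these scales. A needlessly wide interval gives up information that has already been collected. The way baseline is handled here may also carry over to the model tried out for the efficacy trial.

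**Working it through.** **Inputs from the documents.** 1:1 allocation and a target of 60 DR parent units, a dyad counting as one (Statistical Design and Power); 75 recruited and 80% retention (Sample Size). These figures reproduce: 60/0.80 = 75, and 54 × 2 + 6 = 114 individuals. Sixty units give n = 30 per arm. The documents state no SD, pre-post correlation, confidence level or interval width for the scales, so there is no planned precision figure to reproduce.

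**Assumptions.** Two-sided 95% intervals; one score per unit and independent units; equal pre and post SDs; pre-post correlation r varied over a range; pre-program score available.

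**Formulas, in SD units.**

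- Change: half-width = t(58 df) × √[2(1 − r) × 2/n]
- Adjusted (ANCOVA): half-width = t(57 df) × √[(1 − r²) × (2/n) × (1 + 1/(2n − 4))]. The last factor is the average cost of chance baseline imbalance.
- Post-program score alone: half-width = t(58 df) × √(2/n)

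At r = 0.5 and n = 30:

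- Change: 2.0017 × √(1 × 0.0667) = 0.517
- Adjusted: 2.0025 × √(0.75 × 0.0667 × 1.0179) = 0.452
- Ratio: 0.517/0.452 = 1.144

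| r (assumed) | Change | Adjusted | Post only | Change wider than adjusted by |
|---|---|---|---|---|
| 0.3 | 0.612 | 0.498 | 0.517 | 23% |
| 0.5 | 0.517 | 0.452 | 0.517 | 14% |
| 0.7 | 0.400 | 0.373 | 0.517 | 7.5% |
| 0.8 | 0.327 | 0.313 | 0.517 | 4% |
| 0.9 | 0.231 | 0.227 | 0.517 | 2% |
| 0.95 | 0.163 | 0.163 | 0.517 | 0.3% (a tie) |

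A simulation of 4000 data sets at each of four correlations gave ratios of 1.226, 1.144, 1.075 and 1.016 at r = 0.3, 0.5, 0.7 and 0.9, in agreement with the table.

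**Change against ignoring the pre-program score.** The variances are in the ratio 2(1 − r) to 1, so change is the less precise whenever r < 0.5.

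**Unequal SDs.** Let k be the post SD divided by the pre SD. In pre-SD units, the per-unit variance is k² + 1 − 2rk for change and k²(1 − r²) for the adjusted analysis. The difference is (1 − rk)², which is never negative and is zero only when rk = 1, for example k = 1.25 at r = 0.8. In large samples, then, change never does better than adjustment. At 30 per arm and equal SDs it is narrower, by under 1%, only above about r = 0.95, because of the extra degree of freedom and the imbalance factor.

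**The case against.** The strongest objection is that the plan schedules no pre-program score, so as written neither a change score nor an adjusted difference can be computed for these scales. That stands, and it is the more basic gap. It makes the precision point conditional without removing it: the plan's own reference to change presupposes the score, and once the score exists the estimator still has to be chosen.

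Second, a reader might infer that the plan prescribes subtraction as its estimator. The documents do not support that. The phrase is a loose descriptive aim with no formula, and the MMRM to be tried on the pilot data could carry baseline as a covariate or as a response. A baseline-adjusted analysis is therefore neither excluded nor specified. The remedy is the same either way: define it.

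Third, the loss may be small. The program takes about 60 minutes and the post-test follows at once, so a baseline taken just before it could correlate highly with the post-program score. At r = 0.8 to 0.9 the penalty is only 4% to 2%. This is fair, and the documents cannot settle it.

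Fourth, a reader might add chance imbalance at baseline as a further harm. At r = 0.5 a one-SD imbalance of √(2/30) = 0.26 shifts the change estimate by (1 − 0.5) × 0.26 = 0.13 SD. But the excess variance of change over adjustment is (1 − r)² × 2/n, and its square root is the same 0.13. It is the same loss of precision, not a second one, and the change score remains unbiased under randomization.

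Fifth, this is a feasibility pilot with no hypothesis test or power target. Means and SDs by arm are reported separately, so the spread needed to plan the efficacy trial does not depend on how the arm effect is estimated. That also stands.

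**Conclusion.** The point holds in conditional form and is minor. Given a pre-program score, a difference in change is a valid but generally less efficient summary of the arm effect on intention, competence and anxiety. At 30 independent units per arm with equal SDs, its 95% interval is about 23% wider than the adjusted one at r = 0.3, falling to 2% at r = 0.9 and a tie near 0.95. All values of r are assumed.

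It would be too strong to say that adjustment wins at every correlation below 1. That is the large-sample result for equal SDs; at this size the advantage has gone by about 0.95. The absolute widths assume one score per family. Using both parents of a dyad would change them, and the percentages were not worked out for that case. The 60 units are those retained through follow-up, so the immediate post-test may have somewhat more.

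The primary outcome, Yes/No disclosure among parents who had not disclosed at entry, is unaffected, as are the recruitment, retention and acceptability metrics.

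**What to change.** - In the Statistical Analysis Plan, define the effect on intention, competence and anxiety as the arm difference in post-program score adjusted for the pre-program score (ANCOVA or the equivalent mixed model, allowing for dyads), with a 95% confidence interval.
- Show raw change by arm as description only.
- Use the same baseline covariate when the MMRM is tried on the pilot data.
- Reconcile Assignment of Participants, Group Randomized Trial and Delivery of Interventions with the Statistical Analysis Plan by stating when the pre-program score is taken.

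If the scales are already given before the program, the cost is wording and one degree of freedom. If they are not, the plan must either add that administration or drop the references to change for these outcomes.
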